11.8 Appendix 8: Contraceptive Guidance and Collection of Pregnancy Information

Definitions:

Woman of Childbearing Potential (WOCBP)

A woman is considered fertile following menarche and until becoming postmenopausal unless permanently sterile (see below).

Women in the following categories are not considered WOCBP

1. Premenarchal: Note premenarchal females **ARE NOT ELIGIBLE TO PARTICIPATE** in this study.
2. Premenopausal female with 1 of the following:
 - a) Documented hysterectomy.
 - b) Documented bilateral salpingectomy.
 - c) Documented bilateral oophorectomy. Note: Documentation can come from the study center personnel's: review of the patient's medical records, medical examination, or medical history interview.
3. Postmenopausal female:
 - a) Postmenopausal females are defined as amenorrhoeic for greater than 1 year with an appropriate clinical profile, eg. age appropriate, > 45 years, in the absence of hormone replacement therapy.

Contraception Guidance

Male Patients

- Male patients with female partners of childbearing potential are eligible to participate if they agree to ONE of the following from the first dose up to 30 days after the last dose of study medication:
 - Are abstinent from penile-vaginal intercourse as their usual and preferred lifestyle (abstinent on a long-term and persistent basis) and agree to remain abstinent.
 - Agree to use a male condom plus partner use of a contraceptive method with a failure rate of < 1% per year as described in Table 12 when having penile-vaginal intercourse with a woman of childbearing potential who is not currently pregnant.
- In addition, male patients must refrain from donating sperm for the duration of the study and for 30 days after the last dose of study medication.
- Male patients with a pregnant or breastfeeding partner must agree to remain abstinent from penile-vaginal intercourse or use a male condom during each episode of penile penetration during the study and for 30 days after the last dose of study medication.

Female patients

Female patients of childbearing potential are eligible to participate if they are not breastfeeding and agree to use a highly effective method of contraception consistently and correctly as described in the table below, during the study starting at Visit 1 and for at least 30 days after the last dose of study treatment.

Table 12: Highly Effective Contraceptive Methods


Highly Effective Contraceptive Methods That Are User Dependent ^a
 
Failure rate of < 1% per year when used consistently and correctly.

Combined (estrogen and progestogen containing) hormonal contraception associated with inhibition of ovulation^b
 
 • Oral • Intravaginal • Transdermal

Progestogen only hormonal contraception associated with inhibition of ovulation
 
 • Oral • Injectable

Highly Effective Contraceptive Methods That Are User Independent ^a

Implantable progestogen only hormonal contraception associated with inhibition of ovulation^b
 
 • Intrauterine device (IUD) • Intrauterine hormone-releasing system (IUS) 
Bilateral tubal occlusion.

Vasectomized partner
 
A vasectomized partner is a highly effective birth control method provided that the partner is the sole male sexual partner of the WOCBP and the absence of sperm has been confirmed. If not, an additional highly effective method of contraception should be used.

Sexual abstinence
 
Sexual abstinence is considered a highly effective method only if defined as refraining from heterosexual intercourse during the entire period of risk associated with the study treatment. The reliability of sexual abstinence needs to be evaluated in relation to the duration of the study and the preferred and usual lifestyle of the patient.

NOTES:
 
^a Typical use failure rates may differ from those when used consistently and correctly. Use should be consistent with local regulations regarding the use of contraceptive methods for subjects participating in clinical studies.

Table 12: Highly Effective Contraceptive Methods

^bHormonal contraception may be susceptible to interaction with the study treatment, which may reduce the efficacy of the contraceptive method. In this case, 2 highly effective methods of contraception should be utilized during the treatment period and for at least 30 days after the last dose of study treatment.

Pregnancy Testing:

- WOCBP should only be included after a negative highly sensitive pregnancy test.
- Additional pregnancy testing should be performed at times specified in the SoA (Section 1.3).

Pregnancy testing should be performed whenever a menstrual cycle is missed or when pregnancy is otherwise suspected.

Collection of Pregnancy Information***Male patients with partners who become pregnant***

The Investigator will attempt to collect pregnancy information on any male patient's female partner who becomes pregnant while the male patient is in the study. This applies only to male patients who receive ensifentrine.

After obtaining the necessary signed informed consent from the pregnant female partner directly, the Investigator will record pregnancy information on the appropriate form and submit it to the Sponsor within 24 hours of learning of the partner's pregnancy. The female partner will also be followed to determine the outcome of the pregnancy. Information on the status of the mother and child will be forwarded to the Sponsor. Generally, the follow-up will be no longer than 6 to 8 weeks following the estimated delivery date. Any termination of the pregnancy will be reported regardless of fetal status (presence or absence of anomalies) or indication for the procedure.

Female Patients who become pregnant

- The Investigator will collect pregnancy information on any female patient who becomes pregnant while participating in this study. Information will be recorded on the appropriate form and submitted to the Sponsor within 24 hours of learning of a patient's pregnancy.
- The patient will be followed to determine the outcome of the pregnancy. The Investigator will collect follow-up information on the patient and the neonate and the information will be forwarded to the Sponsor. Generally, follow-up will not be required for longer than 6 to 8 weeks beyond the estimated delivery date. Any termination of pregnancy will be reported, regardless of fetal status (presence or absence of anomalies) or indication for the procedure.
- While pregnancy itself is not considered to be an AE or SAE, any pregnancy complication or elective termination of a pregnancy will be reported as an AE or SAE. A spontaneous abortion is always considered to be an SAE and will be reported as such.

- Any post-study pregnancy related SAE considered reasonably related to the blinded study medication by the Investigator will be reported to the Sponsor as described in Section 8.7.5. While the Investigator is not obligated to actively seek this information in former patients, he or she may learn of an SAE through spontaneous reporting.
- Any female patient who becomes pregnant while participating in the study will discontinue blinded study medication and be withdrawn from the study.

11.9 Appendix 9: Liver Safety

Phase III-IV liver chemistry stopping and follow-up criteria have been designed to assure patient safety and evaluate liver event etiology (in alignment with the FDA premarketing clinical liver safety guidance). Phase III-IV liver chemistry stopping criteria 1-5 are defined below. Investigators may at their discretion refer patients meeting liver safety criteria below to a specialist who may determine the appropriate or medically necessary additional or confirmatory laboratory tests or procedures as required by the protocol or otherwise deemed necessary (e.g. liver imaging).

1. ALT \geq 3xULN and bilirubin \geq 2xULN (35% direct bilirubin) (or ALT \geq 3xULN and INR $>$ 1.5, if INR measured).

Note: if serum bilirubin fractionation is not immediately available, withdraw study drug for that patient if ALT \geq 3xULN and bilirubin \geq 2xULN. Serum bilirubin fractionation should be performed if testing is available. If testing is unavailable, record presence of detectable urinary bilirubin on dipstick, indicating direct bilirubin elevations and suggesting liver injury.

2. ALT \geq 8xULN.
3. ALT \geq 5xULN but $<$ 8 xULN persists for \geq 2 weeks.
4. ALT \geq 3xULN if associated with symptoms (new or worsening) believed to be related to hepatitis (such as fatigue, nausea, vomiting, right upper quadrant pain or tenderness, or jaundice) or hypersensitivity (such as fever, rash or eosinophilia).
5. ALT \geq 5xULN but $<$ 8 xULN and cannot be monitored weekly for \geq 2 weeks.

When any of the liver stopping criteria 1-5 is met do the following:

- **Immediately** discontinue blinded study medication/investigational product for that patient.
- Report the event to IQVIA within 24 hours of learning its occurrence.
- Complete the liver event CRF and SAE data collection tool if the event also meets the criteria for an SAE. All events of ALT \geq 3xULN and bilirubin \geq 2xULN (35% direct bilirubin) (or ALT \geq 3xULN and INR $>$ 1.5, if INR measured); INR measurement is not required and the threshold value stated will not apply to patients receiving anticoagulants), termed 'Hy's Law' must be reported as an SAE (excluding studies of hepatic impairment or cirrhosis).

Note: if serum bilirubin fractionation is not immediately available, discontinue blinded study medication/investigational product for that patient if ALT \geq 3xULN and bilirubin \geq 2xULN. Serum bilirubin fractionation should be performed if testing is available. If testing is unavailable, record presence of detectable urinary bilirubin on dipstick, indicating direct bilirubin elevations and suggesting liver injury.

- Complete the liver imaging and/or liver biopsy CRFs if these tests are performed.
- Perform liver event follow-up assessments and monitor the patient until liver chemistries resolve, stabilize, or return to baseline values as described below.
- Discontinue blinded study medication/investigational product after completion of the liver chemistry monitoring as described below.
- Do not restart investigational product.

In addition, for criterion 1:

- Make every reasonable attempt to have patients return to clinic within 24 hours for repeat liver chemistries, liver event follow-up assessments (see below), and close monitoring.
- A specialist or hepatology consultation is recommended.
- Monitor patients twice weekly until liver chemistries (ALT, AST, alkaline phosphatase, bilirubin) resolve, stabilize or return to within baseline values.

For criteria 2, 3, 4, and 5:

- Make every reasonable attempt to have patients return to clinic within 24-72 hours for repeat liver chemistries and liver event follow-up assessments (see below).
- Monitor patients weekly until liver chemistries (ALT, AST, alkaline phosphatase, bilirubin) resolve, stabilize, or return to within baseline values; criterion 5 patients should be monitored as frequently as possible.

Patients with ALT \geq 5xULN and $<$ 8xULN which exhibit a decrease to ALT \geq 3xULN, but $<$ 5xULN and bilirubin $<$ 2xULN without hepatitis symptoms or rash, and who can be monitored for 4 weeks:

- Notify the IQVIA Medical Monitor within 24 hours of learning of the abnormality to discuss patient safety.
- Can continue investigational product
- Must return weekly for repeat liver chemistries (ALT, AST, alkaline phosphatase, bilirubin) until they resolve, stabilize or return to within baseline.
- If at any time these patients meet the liver chemistry stopping criteria, proceed as described above.
- If, after 4 weeks of monitoring, ALT $<$ 3xULN and bilirubin $<$ 2xULN, monitor patients twice monthly until live chemistries normalize or return to within baseline values.

For criteria 1-5, make every attempt to carry out the liver event follow up assessments described below:

- Viral hepatitis serology including
 - Hepatitis A IgM antibody
 - Hepatitis B surface antigen and Hepatitis B Core antibody (IgM)
 - Hepatitis C RNA
 - Cytomegalovirus IgM antibody
 - Epstein-Barr viral capsid antigen IgM antibody (or if unavailable, obtain heterophile antibody or monospot testing).
 - Hepatitis E IgM antibody
- Blood sample for PK analysis, obtained within 72 hours of the last dose. Record the date/time of the PK blood sample draw and the date/time of the last dose of blinded study medication/investigational product prior to blood sample draw on the CRF. If the date or time of the last dose is unclear, provide the patient's best approximation. If the date/time of the last dose cannot be approximated OR a PK sample cannot be collected in the time period indicated above, do not obtain a PK sample. Instructions for sample handling and shipping are in the SPM.
- Serum creatinine phosphokinase (CPK) and lactate dehydrogenase (LDH)
- Fractionate bilirubin, if total bilirubin $\geq 2xULN$
- Obtain complete blood count with differential to assess eosinophilia.
- Record the appearance or worsening of clinical symptoms of hepatitis or hypersensitivity such as fatigue, nausea, vomiting, right upper quadrant pain or tenderness, fever, rash or eosinophilia as relevant on the AE report form.
- Record use of concomitant medications, acetaminophen, herbal remedies, or over the counter medications, or putative hepatotoxins, on the concomitant medications report form.
- Record alcohol use on the liver event alcohol intake case report form.

The following are required for patients with ALT $\geq 3xULN$ and bilirubin $\geq 2xULN$ (35% direct) but are optional for the other abnormal liver chemistries:

- Anti-nuclear antibody, anti-smooth muscle antibody, and Type 1 anti-liver kidney microsomal antibodies and quantitative total immunoglobulin G (IgG or gamma globulins).

- Serum acetaminophen adduct HPLC assay (quantifies potential acetaminophen contribution to liver injury in patients with definite or likely acetaminophen use in the preceding week [James, 2009]. NOTE: not required in China.
- Only in those with underlying chronic hepatitis B at study entry (identified by positive hepatitis B surface antigen): quantitative hepatitis B DNA and hepatitis delta antibody. NOTE: if hepatitis delta antibody assay cannot be performed, it can be replaced with a PCR of hepatitis D RNA virus where needed (Le Gal, 2005).

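### Section 11.9 gives two incompatible times for stopping study drug once a liver stopping criterion is met

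*Protocol*

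**What the plan says.** Section 11.9 defines five liver chemistry stopping criteria and then opens a single list with the words "When any of the liver stopping criteria 1-5 is met do the following". The list has seven bullets, in this order:

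1. "Immediately discontinue blinded study medication/investigational product for that patient" (the word for the timing is in bold in the protocol).
2. "Report the event to IQVIA within 24 hours of learning its occurrence".
3. Complete the liver event form and, where it applies, the SAE tool.
4. Complete the imaging or biopsy forms if those tests are done.
5. "Perform liver event follow-up assessments and monitor the patient until liver chemistries resolve, stabilize, or return to baseline values as described below".
6. "Discontinue blinded study medication/investigational product after completion of the liver chemistry monitoring as described below".
7. "Do not restart investigational product".

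The blocks specific to criterion 1 and to criteria 2-5 come after this list. They set twice-weekly and weekly monitoring respectively, with no maximum duration in either case.

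Section 7.1.2 refers the reader to Section 11.9. It gives no stop time and leaves discontinuation as something for the investigator to weigh.

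**The concern.** A site that follows bullet 1 stops the drug at once. A site that follows bullet 6 keeps dosing until monitoring is finished, which by bullet 5 means until the liver tests have resolved, stabilized or returned to baseline. On that reading the drug is stopped only after the signal has settled, with no upper limit on the delay. The rule covers the combined ALT and bilirubin elevation that the protocol calls Hy's Law, so the stop time matters for patient safety. There is a compliance problem too: one site could defend continued dosing by citing bullet 6, while a monitor citing bullet 1 would record a deviation.

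**Working it through.** No arithmetic applies, so the check is a comparison of texts.

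**Do the two bullets apply to different patients or products?** No. Both name blinded study medication/investigational product, both sit under the same trigger, and neither carries a condition. The criterion-specific blocks start only after the list ends, so they cannot divide the two bullets between groups.

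**Can both be obeyed?** Not as stop times. An immediate stop leaves nothing to discontinue after monitoring. A stop after monitoring is not immediate.

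**How long is the deferral?** It is undefined. Bullet 5 ends monitoring by outcome rather than by date, and the criterion-specific blocks do the same.

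**Which bullet is wrong?** Four features of Section 11.9 support the immediate stop:

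- Bullet 1 comes first and its timing is bolded. Bullet 7 forbids restarting.
- For criterion 1, two notes order the drug stopped without waiting for a further test: "if serum bilirubin fractionation is not immediately available, withdraw study drug for that patient" and "if serum bilirubin fractionation is not immediately available, discontinue blinded study medication/investigational product for that patient". In both, the condition is ALT at least 3 times and bilirubin at least 2 times the upper limit of normal.
- Criterion 5 applies because the patient cannot be monitored weekly for at least 2 weeks. Bullet 6 would tie that patient's stop to completing monitoring that the criterion itself says cannot be done on that schedule.
- The follow-up PK sample is due within 72 hours of the last dose, which fits a prompt stop.

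**Does other text reconcile the two?** No.

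- Section 11.9 has a path that allows treatment to continue, but for a separately defined group: ALT that was at least 5 but below 8 times the upper limit and has fallen to at least 3 but below 5 times, bilirubin below 2 times, no hepatitis symptoms or rash, and able to be monitored for 4 weeks. That path returns anyone who meets a stopping criterion to the list.
- Section 7.1.2 contains no time. Its permissive wording is softer than Section 11.9, whereas Section 7.1.5 uses mandatory wording for a mandatory stop (a positive pregnancy test). But Section 7.1.2 can be read as covering the continue-treatment path as well, so it is a matter of alignment and not a second error.
- Section 7.1 sends patients who must stop drug to the Section 7.3 procedures. Section 7.3.1 and footnote 4 of the Schedule of Activities ask that patients stay on drug through the early termination visit where possible. That qualifier keeps them from overriding Section 11.9, but they do not help a reader settle on the immediate stop.

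**The case against.** The strongest reply is that this is a stray drafting line with little practical effect. Once bullet 1 is followed, bullet 6 has nothing left to act on and bullet 7 prevents a restart. A site would have to pass over the first and most emphasized instruction, and it would still have to report within 24 hours under Section 11.9 and raise immediate safety concerns with the sponsor under Section 8.0. This is largely right and is why the point is not rated higher.

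Exposure is also narrow. The Schedule of Activities places chemistry at Screening, Day 1, Week 24, Week 48 and early termination. Appendix 3 has samples drawn before dosing. Week 24 is the last treatment visit for the 24-week subset, and Week 48 is the last for the 48-week subset. Scheduled tests can therefore raise the conflict while dosing is due to continue mainly through the Day 1 result, or at Week 24 in the 48-week subset of about 400 patients. Unscheduled tests add to this, so exposure is small but not zero.

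Two further points stand in part. The documents do not say what bullet 6 was meant to convey. It might have meant later withdrawal from the study, although it names study medication, and Sections 7.1 and 7.2 do not require study withdrawal after stopping drug except for active COVID-19. The sponsor should confirm the intent. Also, a formal amendment needs ethics approval, and regulatory approval where applicable (Appendix 2), across the 12 countries in SAP Table 3, so the change is not free.

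None of this removes the contradiction.

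**Conclusion.** The concern holds. As written, Section 11.9 sets two incompatible stop times for patients who meet any of liver stopping criteria 1-5, and the deferred one is the error. No numerical effect is claimed: the number of affected patients is not given, and the deferred stop has no stated maximum delay. The conclusion that the immediate stop is intended is an inference from the surrounding text, though a strong one. Harm at a careful site is unlikely. The point should be fixed because it is current operative text in a safety stopping rule, in a trial that admits patients with chronic stable hepatitis B or C (Section 5.2, exclusion 12) and has no data monitoring committee (SAP Section 4.1).

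**What to change.** Delete bullet 6 from the Section 11.9 list. Keep the immediate stop as the only timing, and leave the follow-up, monitoring and no-restart bullets as they are. Leave the continue-treatment path unchanged, since it already returns patients who meet a stopping criterion to the list. The sponsor should confirm that bullet 6 had no other purpose.

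As a secondary alignment, reword Section 7.1.2 along these lines: *Study medication must be stopped immediately in any patient who meets one of liver stopping criteria 1-5 in Section 11.9. The investigator may also stop it whenever this is judged best for the patient.*

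The cost is one deleted bullet and one reworded sentence, with no change to data collection, sample size or analysis. The study has already used clarification letters (the Amendment 4.0 rationale and SAP Section 17.5 refer to them), so a letter may suffice. Otherwise the change can go into the next amendment, with the approvals that requires.

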11.10 Appendix 10: Medical Device Information

Definitions of a Medical Device Incident

The detection and documentation procedures described in this protocol apply to all Sponsor medical devices provided for use in the study (see Section 6.2.2) for the list of Sponsor medical devices).

Medical Device Incident Definition

- A medical device incident is any malfunction or deterioration in the characteristics and/or performance of a device as well as any inadequacy in the labeling or the instructions for use which, directly or indirectly, might lead to or might have led to the death of a patient/user/other person or to a serious deterioration in his/her state of health.
- Not all incidents lead to death or serious deterioration in health. The nonoccurrence of such a result might have been due to other fortunate circumstances or to the intervention of health care personnel.

It is sufficient that:

- An incident associated with a device happened.

AND

- The incident was such that, if it occurred again, might lead to death or a serious deterioration in health.

A serious deterioration in state of health can include any of the following:

- Life-threatening illness.
- Permanent impairment of body function or permanent damage to body structure.
- Condition necessitating medical or surgical intervention to prevent 1 of the above.
- Fetal distress, fetal death, or any congenital abnormality or birth defects.

Examples of Incidents

- A patient, user, caregiver, or healthcare professional is injured as a result of a medical device failure or its misuse.
- A patient's blinded study medication is interrupted or compromised by a medical device failure.
- A misdiagnosis due to medical device failure leads to inappropriate treatment.
- A patient's health deteriorates due to medical device failure.

Documenting Medical Device Incidents

Medical Device Incident Documenting

- Any medical device incident occurring during the study will be documented in the patient's medical records, in accordance with the Investigator's normal clinical practice, and on the appropriate form of the CRF.
- For incidents fulfilling the definition of an AE or an SAE, the appropriate AE/SAE CRF page will be completed as described in Section 11.7.
- The CRF will be completed as thoroughly as possible and signed by the Investigator before transmittal to the Sponsor or designee.
- It is very important that the Investigator provides his/her assessment of causality (relationship to the medical device provided by the Sponsor) at the time of the initial AE or SAE report and describes any corrective or remedial actions taken to prevent recurrence of the incident.
- A remedial action is any action other than routine maintenance or servicing of a medical device where such action is necessary to prevent recurrence of an incident. This includes any amendment to the device design to prevent recurrence.

